Between clinic visits 1 and 2, participants will complete the daily WURSS-21 questionnaire to assess respiratory symptoms. If they have no symptoms, they will not need to complete this questionnaire.

Blood will be collected for the following measurements:

Sample	Measurement	Analysed by	Reason
Blood	Full blood count	University Hospital Southampton Chemical Pathology	Reports blood immune cell numbers (plus red cells and platelets)
Blood – Serum	TNF $\alpha$ IL-1 $\beta$ IL-1RA IL-4 IL-6 IL-8 IL-10 IL-17 IFN- $\gamma$ GM-CSF sCD14 IFN $\alpha/\beta$	University of Birmingham	Inflammatory markers
Blood - Serum	Insulin  Total cholesterol HDL- cholesterol LDL- cholesterol Triglycerides  25-hydroxyvitamin D3 Calcium	University Hospital Southampton Chemical Pathology	Glucose homeostasis  Blood lipids  Vitamin D status
Blood - Serum	Leptin Adiponectin Visfatin Resistin  CRP LPS binding protein	University of Southampton	Adipose tissue function markers  Inflammatory markers

Blood - plasma	Parathyroid hormone Glucose	University Hospital Southampton Chemical Pathology	Related to vitamin D status Glucose homeostasis
Blood - plasma	Zonulin-1 Occludin iFABP Citrulline sCD14	University of Southampton	Gut integrity markers
Blood mononuclear cells	Differentiated CD57+ve NK cells T cells PTK7+ve recent thymic emigrant cells Naïve memory T cells (CD3+ve but differential expression of CD45RA, CD28, CD57 and KLRG1) Regulatory T cells (FOXP3 and CD25+ve) B cells (CD24hi, CD38hi)	University of Birmingham	Immune cell phenotypes
Urine	Metabolome	University of Southampton	Microbiota and diet- related metabolome
Faeces	Whole genome shotgun metagenomics, and metabolomic analysis Wet/dry weight	Quadram Institute	Quantitative intestinal microbiome profiling

Volumes of blood to be collected will be as follows:

Matrix	Collection tube	Volume	Analytes
Serum	SST	~ 3.5 ml	Insulin
Serum	SST	~ 5 ml	CRP, cholesterol, HDL, LDL, triglycerides, vitamin D, calcium
Serum	SST	~ 3.5 ml	Leptin, adiponectin, visfatin, resistin
Serum	Red top serum	~ 6 ml	TNF $\alpha$ , IL-1 $\beta$ , IL-1RA, IL-4, IL-6, IL-8, IL-10, IL-17, IFN- $\gamma$ , GM-CSF, IFN $\alpha/\beta$
Blood mononuclear cells	Lithium heparin	~ 18 ml (3 x 6 ml)	Immune cell phenotypes
Plasma	Fluoride oxalate	~ 5 ml	Glucose
Plasma	EDTA	~ 6 ml	Zonulin-1, Occludin, iFABP, Citrulline, sCD14
Blood	EDTA	~ 3.5 ml	Full blood count
Plasma	Lithium heparin	~ 6 ml	Parathyroid hormone

[figure not shown]

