A summary of the questionnaires to be used at each time point is as follows:

Questionnaire	V1 (baseline)	V2 (3 months)
Food frequency (EPIC and 3 x intake 24)	YES	YES
Quality of life (EQ5D5L)	YES	YES
Physical activity (PASE)	YES	YES
Respiratory symptoms (WURSS-21)	Daily between V1 and V2 (Only if participant has symptoms)	

### Visit 2

Three months ( $12 \pm 1$  weeks) after Visit 1, participants will return to the NIHR Clinical Research Facility at University Hospital Southampton for visit 2 (V2). Participants will be asked to bring a recent faecal sample and three recent urine samples with them; these will have been collected and stored in the same way as for post-V1 and again a 3 day food diary will be completed. All measurements, blood samples and questionnaires conducted at visit 1 will be repeated at visit 2.

Figure 2. Further overview of the study plan.

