#### 4. Variables and analyses

The primary outcomes measured will be vitamin D status (measured as 25-hydroxyvitamin D3 in serum), colonisation of the probiotic organism (measured as numbers of *L. plantarum* in faeces), and serum CRP concentration (measured with a high sensitivity kit).

In addition, the following will be measured as secondary outcomes:

1. Immune cell phenotypes
2. Inflammatory markers
3. Faecal microbiome taxonomy
4. Weight, body mass index, body fat mass, body lean mass, hip circumference, waist:hip ratio
5. Grip strength
6. Dietary intake (from food frequency questionnaire)
7. Quality of life (questionnaire)
8. Physical activity (questionnaire)
9. Respiratory symptoms (questionnaire)
10. Blood glucose, insulin, HOMA-IR
11. Blood lipids (total, LDL and HDL cholesterol, triglycerides)
12. Blood adipokines (leptin, adiponectin, leptin/adiponectin ratio, visfatin and resistin)
13. Blood markers of intestinal barrier integrity
14. Blood PTH and calcium, as markers of vitamin D homeostasis
15. Faecal metabolome
16. Urinary metabolome

Serum calcium and plasma parathyroid hormone will be measured as these relate to vitamin D status and action.

Full blood count will be conducted to obtain absolute numbers of different types of immune cells.

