#### 5. Sample size and statistical analysis

The primary outcomes of the study are serum 25-hydroxyvitamin D3 concentration, colonisation with the probiotic organism (as detected in faeces), and serum CRP concentration. The study sample size has been calculated based upon blood 25-hydroxyvitamin D3 concentration. Assuming a study entry concentration of 45 nmol/l and an increase to 70 nmol/l after receiving 10 µg/day calcifediol for 3 months (both with a standard deviation of 25 nmol/l), a sample size of 72 (n = 36 per group i.e. + or – vitamin D) will give 95% power to detect the difference in concentrations as significant at  $p < 0.01$ . To allow for a drop-out rate of 30% a total of 104 participants will be enrolled. This sample size will be sufficient to detect colonisation with the probiotic, as such colonisation (with other organisms) has been shown with smaller sample sizes. Using our data for serum CRP concentrations in older people resident in care homes (mean 6.3 ± 2.2 mg/dl) we estimate that a sample size of study completers of 36 per group will give 70% power to detect a 20% reduction as significant.

Changes between V1 and V2 in all outcomes will be compared between groups by ANOVA for 2 x 2 factorial design; subsequent pairwise comparisons between groups will be performed. Statistical analysis will be conducted using the current version of SPSS.

Study materials (i.e. the supplements) will be provided prepackaged by DSM. DSM will allocate a study ID to each participant's package of supplements in order that both participants and researchers are blind to allocation. DSM will provide to the researchers a sealed envelope (one per participant) containing the treatment allocation for each participant. These envelopes will be kept in a locked filing cabinet and will be accessed a) if there is a SAE and b) once the database is complete and locked and prior to statistical analysis being performed.

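### WURSS-21 has no V1 or V2 value, so the V1-to-V2 change analysis cannot be applied to it, and its symptomatic-days-only recording makes a blank day ambiguous

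*Protocol*

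**What the plan says.** Section 4 of the Protocol lists "Respiratory symptoms (questionnaire") as item 9 of 16 secondary outcomes.

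Section 3 describes its collection: "Between clinic visits 1 and 2, participants will complete the daily WURSS-21 questionnaire to assess respiratory symptoms". The next sentence limits this: "If they have no symptoms, they will not need to complete this questionnaire". The questionnaire summary table repeats the limit: "Daily between V1 and V2 (Only if participant has symptoms"). In that table the dietary, quality-of-life and physical-activity questionnaires are each marked for both V1 and V2. WURSS-21 is marked for neither. The repeat rule for the second visit is "All measurements, blood samples and questionnaires conducted at visit 1 will be repeated at visit 2", and WURSS-21 is not among the questionnaires administered at V1.

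Section 5 gives one analysis for everything: "Changes between V1 and V2 in all outcomes will be compared between groups by ANOVA for 2 x 2 factorial design". It makes no exception for respiratory symptoms.

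Two other provisions in section 3 matter here. Participants keep a daily paper diary of supplement use. They start the supplement only after producing the faecal and urine samples, which are to be collected within a week of V1.

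**The concern.** The analysis rule needs two measurements per participant, one at each visit. For WURSS-21 the schedule provides neither, so the only stated analysis of this outcome cannot be carried out.

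The recording rule raises a separate difficulty. Symptom-free days leave no record, and neither do days on which an ill participant did not fill in the form. A later analysis plan can choose how to score blanks, but it cannot recover which kind of blank each one was. The information has to be collected at the time.

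WURSS-21 is the only listed outcome dedicated to respiratory illness, and the introduction gives susceptibility to infection in older people as part of the rationale. If reporting fell off more in one group than another and blanks were read as wellness, that group would appear to have had less illness.

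**Working it through.** **1. Can the change be formed?** Setting the provisions side by side:

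| Questionnaire | V1 value | V2 value | V1-to-V2 change |
|---|---|---|---|
| Food frequency / intake | yes | yes | can be formed |
| EQ5D5L | yes | yes | can be formed |
| PASE | yes | yes | can be formed |
| WURSS-21 | none | none | cannot be formed |

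The V2 repeat rule does not supply the missing value, because it covers only what was done at V1.

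**2. What does a blank mean?** Under the recording rule:
- symptoms and form completed: an entry;
- no symptoms: blank;
- symptoms but form skipped: blank;
- participant has left the trial: blank.

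Three different states share one record. The third cannot be identified from the form.

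**3. How many days could be involved through dropout?** The Protocol gives no figure for WURSS-21, so the only stated input is the dropout allowance: "To allow for a drop-out rate of 30% a total of 104 participants will be enrolled". That figure reproduces: 36 / 0.70 = 51.4, rounded up to 52 per group, and 2 × 52 = 104. This leaves room for 104 − 72 = 32 non-completers.

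Let *d* be the proportion dropping out and *f* the fraction of follow-up completed before leaving. The timing of leaving is an assumption.

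Unobserved share of person-days = *d* × (1 − *f*)

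- Leavers stop half-way (*f* = 0.5): 0.30 × 0.5 = 0.15, or 15%.
- Leavers stop at once (*f* = 0): 0.30 × 1 = 0.30, or 30%.

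If every blank were scored as zero and the symptom rate were the same throughout, the recorded symptomatic days would be 85% or 70% of the true number.

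**4. Does this distort the comparison between groups?** With no true effect, the apparent ratio of symptomatic days is

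[1 − *d*₁(1 − *f*)] / [1 − *d*₀(1 − *f*)]

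With 30% dropout in both groups and *f* = 0.5 this is 0.85 / 0.85 = 1.00. The ratio is distorted only when dropout (or, by the same reasoning, skipping) differs by group.

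**5. Days before the first dose.** Follow-up is 12 weeks × 7 = 84 days, and sampling takes up to about 7 of them: 7 / 84 = 8.3%. No one has taken any product on these days, and the sampling rule is the same in every group. Keeping them would pull a real effect towards no difference but would not favour a group.

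**The case against.** A reader might infer that dropouts are counted as healthy. The Protocol does not say so. It gives no scoring rule for blank days, and such rules are commonly left to a statistical analysis plan, which is not at hand. Dropouts can be identified because they do not attend V2, and could be censored. The one stated analysis needs a V2 value, which points towards leaving non-completers out. This objection stands: the dropout figures describe what would happen if blanks were scored as zero, not what is planned.

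A reader might also infer that there is no usable denominator, or that pre-dose days are treated as on-treatment. Neither is stated. The supplement diary should show roughly which days a participant was still recording and when dosing began. The Protocol sets a collection window for WURSS-21, not an analysis window.

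A specific false reduction in illness might be quoted. For example, dropout of 40% in one group and 20% in another, with half-way leaving, gives 0.80 / 0.90 = 0.89, an apparent 11% reduction. That needs blanks scored as zero, leavers retained in the analysis, and a two-fold dropout imbalance. Nothing in this double-blind trial suggests the last.

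Two points survive. The supplement diary can show that someone was still recording capsules, but not that a blank WURSS-21 day was symptom-free; the week 4 and week 8 contacts have no stated symptom check. So skipped entries by participants who remain in the trial stay undetectable. And the mismatch between the schedule and the change rule lies within the Protocol itself. The days between V1 and first dose are not defined as a baseline, and nothing sets the V1 score to zero.

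**Conclusion.** The point holds in two parts. The V1-to-V2 change analysis cannot be applied to WURSS-21, because neither end of the change is measured; this follows from the text and needs no assumption. The recording rule also makes a symptom-free day and a skipped entry identical, which no later analysis plan can undo.

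The size of the second part cannot be fixed from the Protocol. As an illustration, about 15% of person-days would be unobserved through dropout, assuming the planned 30% and half-way leaving; skipping by retained participants would add an unknown amount. This becomes a bias between groups only if blanks are scored as zero and dropout or skipping differs by group. The pre-dose days, up to about 8% of the window, would dilute an effect if kept and would not create one.

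One secondary outcome is affected. The three primary outcomes and the sample size are not. The change should be made, and it has to be made before data collection to be of use.

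**What to change.** 1. In section 3, add a daily yes/no item on respiratory symptoms to the supplement diary that participants already complete, with WURSS-21 filled in on the yes days. A blank then means missing.
2. In section 5, exempt WURSS-21 from the V1-to-V2 change rule.
3. In section 5, state that groups will be compared on a follow-up summary from first dose to V2, such as symptomatic days or summed score per observed diary day, within the same 2 x 2 factorial framework. The exact model can be left to the statistical analysis plan.

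The cost is one tick per day on an existing diary and about two sentences in section 5. The downside is a slight extra daily burden on participants. No change to recruitment numbers is needed.

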#### 4. Variables and analyses

The primary outcomes measured will be vitamin D status (measured as 25-hydroxyvitamin D3 in serum), colonisation of the probiotic organism (measured as numbers of *L. plantarum* in faeces), and serum CRP concentration (measured with a high sensitivity kit).

In addition, the following will be measured as secondary outcomes:

1. Immune cell phenotypes
2. Inflammatory markers
3. Faecal microbiome taxonomy
4. Weight, body mass index, body fat mass, body lean mass, hip circumference, waist:hip ratio
5. Grip strength
6. Dietary intake (from food frequency questionnaire)
7. Quality of life (questionnaire)
8. Physical activity (questionnaire)
9. Respiratory symptoms (questionnaire)
10. Blood glucose, insulin, HOMA-IR
11. Blood lipids (total, LDL and HDL cholesterol, triglycerides)
12. Blood adipokines (leptin, adiponectin, leptin/adiponectin ratio, visfatin and resistin)
13. Blood markers of intestinal barrier integrity
14. Blood PTH and calcium, as markers of vitamin D homeostasis
15. Faecal metabolome
16. Urinary metabolome

Serum calcium and plasma parathyroid hormone will be measured as these relate to vitamin D status and action.

Full blood count will be conducted to obtain absolute numbers of different types of immune cells.

#### 5. Sample size and statistical analysis

The primary outcomes of the study are serum 25-hydroxyvitamin D3 concentration, colonisation with the probiotic organism (as detected in faeces), and serum CRP concentration. The study sample size has been calculated based upon blood 25-hydroxyvitamin D3 concentration. Assuming a study entry concentration of 45 nmol/l and an increase to 70 nmol/l after receiving 10 µg/day calcifediol for 3 months (both with a standard deviation of 25 nmol/l), a sample size of 72 (n = 36 per group i.e. + or – vitamin D) will give 95% power to detect the difference in concentrations as significant at  $p < 0.01$ . To allow for a drop-out rate of 30% a total of 104 participants will be enrolled. This sample size will be sufficient to detect colonisation with the probiotic, as such colonisation (with other organisms) has been shown with smaller sample sizes. Using our data for serum CRP concentrations in older people resident in care homes (mean 6.3 ± 2.2 mg/dl) we estimate that a sample size of study completers of 36 per group will give 70% power to detect a 20% reduction as significant.

Changes between V1 and V2 in all outcomes will be compared between groups by ANOVA for 2 x 2 factorial design; subsequent pairwise comparisons between groups will be performed. Statistical analysis will be conducted using the current version of SPSS.

Study materials (i.e. the supplements) will be provided prepackaged by DSM. DSM will allocate a study ID to each participant's package of supplements in order that both participants and researchers are blind to allocation. DSM will provide to the researchers a sealed envelope (one per participant) containing the treatment allocation for each participant. These envelopes will be kept in a locked filing cabinet and will be accessed a) if there is a SAE and b) once the database is complete and locked and prior to statistical analysis being performed.

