After blood collection, participants will be given breakfast (orange juice, toast and jam, tea or coffee). Following consumption of breakfast, participant's diet will be assessed using the widely used EPIC Food Frequency Questionnaire, their quality of life will be assessed using EQ5D5L and their physical activity will be assessed using PASE. Participants will then be randomised to one of four groups (vitamin D (calcifediol, 10 µg/day), probiotic (*Lactobacillus plantarum* TIFN101 (5 x 10^9 cfu/day)), vitamin D + probiotic, or placebo) and will receive 3 months supply along with a diary to record that they have taken their supplement each day. Blinding, randomisation, and supplement packaging will be completed by individuals independent of the researchers involved in the study. Participants will be randomised stratified by sex to ensure equal numbers of males and females in each treatment group.

Participants will also take away materials for collection of faecal and urine samples. They will be provided with a pack and instructions for collecting a faecal sample and 3 urine samples at home within one week of V1. Two urine samples will be collected on weekdays (one per day) and one urine sample will be collected at a weekend or first thing on a Monday morning. Participants will be asked to complete a 24 hr food diary using the online tool 'intake 24' or by completing a

paper diary 24 hr prior to collecting each urine sample. Participants will be asked to keep the urine samples in their home fridge until all 3 samples have been collected. Participants will be asked to collect a faecal sample within 24 hours of the last urine collection. Participants will be asked to either return their samples to the Clinical Research Facility in person or to contact the researcher once samples are available who will travel to their home to collect the samples or will arrange for them to be collected by courier.

At the end of V1 participants will be provided with their supplements and instructed to start taking these once they have produced their faecal sample and three urine samples. Participants will receive instructions on taking their supplements and will record this daily use in a paper diary.

Participants will be contacted every 4 weeks by the researcher (at week 4 and week 8) and will be requested to bring unused supplements to their end of study clinic visit (visit 2; week 12). These will be used to assess compliance.

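### The protocol analyses unadjusted V1–V2 changes but sizes the trial on single-time concentrations, so its stated powers rest on an unstated V1–V2 correlation, and baseline adjustment would recover precision at almost no cost

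*Protocol*

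**What the plan says.** Protocol section 5 (Sample size and statistical analysis) sets one model for every outcome, the three primary outcomes included: "Changes between V1 and V2 in all outcomes will be compared between groups by ANOVA for 2 x 2 factorial design". Pairwise comparisons between groups follow. The section names no covariate.

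The sample size in the same section is built on serum 25-hydroxyvitamin D3: "Assuming a study entry concentration of 45 nmol/l and an increase to 70 nmol/l after receiving 10 µg/day calcifediol for 3 months", with "both with a standard deviation of 25 nmol/l". The conclusion is that "a sample size of 72 (n = 36 per group", with and without vitamin D) "will give 95% power to detect the difference in concentrations as significant" at p<0.01. For CRP the inputs are "mean 6.3 ± 2.2 mg/dl", a 20% reduction, 36 completers per group and 70% power.

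Section 3 (Visit 1) describes the allocation: "Participants will be randomised stratified by sex to ensure equal numbers of males and females in each treatment group".

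The protocol gives neither a correlation between V1 and V2 nor a standard deviation of change for any outcome.

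**The concern.** The power statement and the analysis refer to different quantities. The power is computed for a comparison of concentrations measured once, whereas the test compares changes. The standard deviation of a change depends on the V1–V2 correlation and equals the single-time value only when that correlation is 0.5. The stated 95% and 70% therefore belong to the planned analysis only under an assumption that the protocol does not make.

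A change score also fixes the coefficient on the V1 value at 1. When the true regression slope of V2 on V1 is smaller, this over-corrects for baseline and adds noise. The V1 values of 25-hydroxyvitamin D and CRP are collected in any case, so the lost precision is avoidable. CRP has the least to spare, because its claimed power is only 70%.

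Sex was judged important enough to stratify on, yet it does not appear in the model. This is a supporting point only, since the protocol gives no figure from which to size the loss.

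**Working it through.** **Inputs from protocol section 5.** 25-hydroxyvitamin D: difference 70 − 45 = 25 nmol/l (taking the untreated groups to stay at 45), SD 25 at each visit, 36 per margin, alpha 0.01. CRP: difference 0.20 × 6.3 = 1.26, SD 2.2 (reading the ± as an SD), 36 per group. No alpha is stated for CRP, so two-sided 5% is assumed.

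**Reproducing the plan's figures.** For two means with a two-sided test, n per group = 2 × (2.576 + 1.645)² × (25/25)² = 35.6, so 36. Power with 36 per group is 95.2% by the normal approximation and 94.1% by the noncentral t. Dropout: 72/0.70 = 102.9, so 103; the stated 104 is the next multiple of four cells. CRP power is 68.1% (normal) or 66.9% (noncentral t), close to the stated 70%. The figures reproduce, but for single-time concentrations.

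**Formulas for the two analyses**, with equal V1 and V2 variances and correlation r:

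- SD of change = SD × √(2(1 − r))
- Baseline-adjusted SD = SD × √(1 − r²)
- Variance ratio, ANCOVA to change = (1 − r²)/(2(1 − r)) = (1 + r)/2

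**Results.** These use the noncentral t with 36 per margin and 68 degrees of freedom for change or 67 for ANCOVA. The values of r are assumptions. Equal variances are stated for 25-hydroxyvitamin D but assumed for CRP.

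| r | SD of change / adjusted SD (nmol/l) | 25(OH)D power, change v ANCOVA | CRP power, change v ANCOVA | Variance ratio |
|---|---|---|---|---|
| 0.2 | 31.6 / 24.5 | 76% v 95% | 47% v 69% | 0.60 |
| 0.3 | 29.6 / 23.8 | 82% v 96% | 53% v 71% | 0.65 |
| 0.5 | 25.0 / 21.7 | 94% v 99% | 67% v 79% | 0.75 |
| 0.6 | 22.4 / 20.0 | 98% v 99.5% | 76% v 85% | 0.80 |
| 0.7 | 19.4 / 17.9 | 99.7% v 99.9% | 87% v 92% | 0.85 |

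A sex term takes one more degree of freedom, which leaves these figures unchanged to the precision shown.

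By the normal approximation, 95% power for 25-hydroxyvitamin D under the change analysis needs 50 per group at r=0.3, 36 at r=0.5 and 22 at r=0.7. Under ANCOVA it needs 33, 27 and 19.

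**Chance baseline imbalance.** On the 36 v 36 margin, the baseline difference in 25-hydroxyvitamin D has SD 25 × √(2/36) = 5.9 nmol/l. Given an imbalance, the change-score estimate moves by −(1 − r) times it. At r=0.5, a one-SD imbalance shifts the estimate by 0.5 × 5.9 = 2.9 nmol/l, against a planned effect of 25. For the pairwise comparisons, with about 18 completers per cell, the corresponding figures are 25 × √(2/18) = 8.3 and 4.2 nmol/l.

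**Validity.** A simulation of 20,000 trials with no treatment effect at r=0.5 gave a mean change-score difference of 0.02 nmol/l and a type I error of 0.0101 at nominal 0.01. The slope of the estimate on the baseline imbalance was −0.50, as the formula predicts.

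**The case against.** The strongest reply is that nothing in the planned analysis is invalid. In a randomised trial the change score is unbiased and keeps its error rate, and the simulation confirms this. A reader might infer that regression to the mean biases the comparison; it does not. It acts only through chance imbalance, and on the margin used for the main effects a typical imbalance moves the estimate by a small part of the planned effect. This stands.

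The power argument is conditional. Above r of about 0.5 the change analysis meets or exceeds the stated powers, reaching 98% for 25-hydroxyvitamin D and 76% for CRP at r=0.6. The protocol contains nothing from which r can be read. This also stands, and it limits the point to an unstated assumption and an efficiency loss.

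The omission of sex is not shown to cost anything measurable. Leaving out a stratification factor generally makes standard errors too large if the factor is prognostic; it does not invalidate the test. An analysis plan that is not available here might name covariates. That answer is weaker for the model as a whole, because the protocol itself commits every outcome to a comparison of changes.

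Finally, ANCOVA is not a remedy for everything. The WURSS-21 is completed only between the visits and has no V1 value. The equal-variance assumption is stated only for 25-hydroxyvitamin D and may fail for others, such as faecal *L. plantarum* numbers. A raw-scale linear model should not be imposed on metagenomic or metabolomic data. The fix is limited accordingly.

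**Conclusion.** The point holds as a mismatch between sample size and analysis, and as an avoidable loss of precision. With equal variances at the two visits, the change-score ANOVA has a larger variance than baseline-adjusted ANCOVA at any realistic r: ANCOVA's variance is lower by 40% at r=0.2, 25% at r=0.5 and 15% at r=0.7. The stated powers carry over to the planned test only if r is about 0.5 or more. Below that, power falls to 82% for 25-hydroxyvitamin D and 53% for CRP at r=0.3, while ANCOVA keeps 96% and 71%.

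A reader might conclude that the trial is underpowered. The protocol does not support that: r is unknown, and the plan's n is correct for the comparison of concentrations that it describes. A shortfall is possible but not demonstrated. The algebra is firm. The power figures rest on the assumed r, on equal variances (an assumption for CRP) and on a two-sided 5% level for CRP.

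**What to change.** In section 5, replace the sentence on ANOVA of changes with wording along these lines: *For continuous outcomes measured at both visits, including 25-hydroxyvitamin D3 and CRP, the V2 value (or the change) will be analysed by a linear model with the two factors (calcifediol, probiotic), their interaction, the V1 value and sex, on a scale suited to the outcome. Adjusted differences will be reported with 95% confidence intervals.* Adjusting for V1 gives the same treatment estimate whether V2 or the change is the response, so the focus on change can be kept.

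State separately how outcomes without a V1 value (WURSS-21) and high-dimensional outcomes (metagenomics, metabolomes) are handled; they lie outside this change.

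In the sample-size paragraph, state the assumed V1–V2 correlation or SD of change behind each power figure, with its source.

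The cost is a few sentences and two degrees of freedom (V1 value and sex). The data are already collected, the model runs in the software the protocol names, and no participants or visits are added.

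### The factorial ANOVA on 25(OH)D change names no covariates, so precision may be lost that baseline, sex and (if recruitment spans seasons) V1 date could recover

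*Protocol*

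**What the plan says.** Protocol section 5 gives one model for every outcome: "Changes between V1 and V2 in all outcomes will be compared between groups by ANOVA for 2 x 2 factorial design", followed by pairwise comparisons of the groups. No baseline value, stratification factor or calendar term is named.

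The sizing rests on one outcome: "The study sample size has been calculated based upon blood 25-hydroxyvitamin D3 concentration". The effect is put as a rise over the study period: "Assuming a study entry concentration of 45 nmol/l and an increase to 70 nmol/l after receiving 10 µg/day calcifediol for 3 months". The same spread, an SD of 25 nmol/l, is taken at entry and at the end. The result is 36 completers on each vitamin D margin, 72 in all, and the claim is that this number "will give 95% power to detect the difference in concentrations", tested at the 1% level. Enrolment is then raised to cover losses: "To allow for a drop-out rate of 30% a total of 104 participants will be enrolled".

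Section 3 (Visit 1) stratifies randomisation by sex only. V2 is the "end of study clinic visit (visit 2; week 12"), and the Visit 2 text allows one week either side. The protocol states no recruitment period and does not mention seasonal variation in 25(OH)D.

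**The concern.** An analysis of raw change with no covariates leaves in the residual whatever pre-treatment information could have explained. Three such items exist for everyone at no extra cost: the V1 value, sex and the V1 date.

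The date deserves separate thought for this outcome. If vitamin D status follows a yearly cycle, a 12-week change does not cancel it, because 12 weeks is close to a quarter of the cycle. Participants who enter on the rising limb drift up and those who enter on the falling limb drift down. Randomised arms share this drift, so it adds noise and not bias. The baseline value removes only part of it, since the same seasonal level can precede a rise or a fall.

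The stake is the width of the confidence intervals. It is smallest for the vitamin D main effect, which is comfortably powered. It is largest for the pairwise comparisons, which bear on the section 2 objective of effects alone and together.

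**Working it through.** **1. The plan's own figure.** Difference 25 nmol/l (70 − 45), SD 25, two-sided 0.01, power 95%:

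n per margin = 2 × (2.576 + 1.645)² × (25/25)² = 35.6, so 36. This matches. Power at 36 v 36 is 95.2% (normal) or 94.1% (noncentral t). Dropout: 72/0.70 = 102.9, so 103; 104 is the next multiple of four. The sizing takes no credit for covariates and does not need any.

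The 25 nmol/l is the SD at each time point, and the SD of change is not given. With equal SDs, SD of change = 25 × √(2(1 − ρ)), which equals 25 only if the V1–V2 correlation ρ is 0.5. Steps 2, 4 and 5 take 25 as an assumption.

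**2. Pairwise comparisons.** 72/4 = 18 completers per arm. SE = 25 × √(2/18) = 8.33 against 25 × √(2/36) = 5.89 on the margin. With the same difference and alpha (the protocol sets no separate alpha for these) and pooled error, the noncentrality is 25/8.33 = 3.0 and power is about 64%.

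**3. Gain from baseline.** Residual SD under ANCOVA = 25 × √(1 − ρ²), so its ratio to the SD of change is √((1 + ρ)/2).

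| ρ (assumed) | SD of change | ANCOVA SD | SE cut |
|---|---|---|---|
| 0.3 | 29.6 | 23.8 | 19% |
| 0.5 | 25.0 | 21.7 | 13% |
| 0.7 | 19.4 | 17.9 | 8% |

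At ρ = 0.5, main-effect power goes from 94.1% to 98.6%. Pairwise noncentrality becomes 25/(21.65 × √(2/18)) = 3.46, and pairwise power goes from about 64% to about 79%.

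**4. Does baseline stand in for season?** For a yearly sine cycle and a 12-week lag, the seasonal levels at V1 and V2 correlate at cos(2π × 12/52) = 0.12. The V1 seasonal level and the seasonal change correlate at −sin(π × 12/52) = −0.66, and 0.66² = 0.44. So baseline captures at most 44% of the seasonal change, and less in practice because measured baseline is mostly non-seasonal variation.

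**5. Gain from date terms alone.** Assumptions not in the documents: entry spread evenly over the year, the same drift in all arms, SD of change 25 including season, amplitude A (half of peak to trough).

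Seasonal SD of change = 2A × sin(π × 12/52)/√2; share = (that SD)²/625; SE ratio = √(1 − share); equivalent completers = 72/(1 − share).

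| A (nmol/l) | Seasonal SD | Share | SE cut | Equivalent completers | Main-effect power | Pairwise power |
|---|---|---|---|---|---|---|
| 5 | 4.7 | 3.5% | 2% | 75 | 94.9% | 66% |
| 10 | 9.4 | 14.1% | 7% | 84 | 97.0% | 72% |
| 15 | 14.1 | 31.7% | 17% | 105 | 99.2% | 83% |

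If everyone entered within a few weeks, the V1 date would barely vary and the gain would be about nil.

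**6. Both together.** Total SD 25 at each visit, A = 10, non-seasonal correlation 0.5. Seasonal variance is 10²/2 = 50, leaving 575; the V1–V2 covariance is 575 × 0.5 + 50 × 0.12 ≈ 294.

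| Model | Residual SD | Main-effect power |
|---|---|---|
| Change, no covariate | √(1250 − 2 × 294) ≈ 25.7 | 92.6% |
| Plus date terms | √(2 × 575 × 0.5) = 24.0 | 95.9% |
| Baseline only | √(625 − 294²/625) ≈ 22.1 | 98.3% |
| Baseline and date | √(575 × 0.75) = 20.8 | 99.2% |

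Baseline is the larger omission here. Date terms on top of baseline cut the SE by a further 6% (1 − 20.8/22.1). At a non-seasonal correlation of 0.8 the further cut is 14%.

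**The case against.** The strongest reply is that covariates are commonly left to the SAP, which is not shown, and that section 5 names a valid analysis without excluding further terms. That is a fair reason to rate the point low. It does not remove it: the sentence names a specific model for every outcome, and a better one is available from data already collected.

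A second reply is that the seasonal loss is assumed. This stands. The documents give no amplitude, recruitment window or SD of change. An amplitude of 15 nmol/l would be a 30 nmol/l swing, larger than the planned effect of 25, and nothing in the protocol supports it.

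A third is that the main effect already has 94% to 95% power. This also stands for that contrast, but not for the pairwise ones.

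A reader might infer more: that season biases the vitamin D effect, that the sample size is wrong, that precision is certainly being thrown away, or that baseline is useless against season. The documents support none of these. Randomisation balances entry date in expectation, the sizing reproduces, the loss is conditional, and baseline takes up to 44% of the seasonal change under the sine model.

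**Conclusion.** The point holds as a minor, precision-only improvement. The planned ANOVA is unbiased and adequately powered for the vitamin D main effect, but it leaves out pre-treatment information that could narrow the intervals.

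Baseline is the surer gain: an SE cut of 8% to 19% for V1–V2 correlations of 0.7 to 0.3. The date gain is conditional, from about nil with a short recruitment window to 2% to 17% with year-round entry and amplitudes of 5 to 15 nmol/l. The pairwise comparisons benefit most, since their power is about 64% if the SD of change is 25 nmol/l. Gains for PTH and respiratory symptoms are plausible but cannot be sized from the protocol.

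**What to change.** Pre-state a 2 x 2 factorial ANCOVA for 25(OH)D and for PTH, with the V1 value and sex as covariates. If recruitment spans more than one season, add sine and cosine of the V1 date. Base the pairwise comparisons on the same model. Settle this before the allocation envelopes are opened, which section 5 places after database lock and before analysis.

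If respiratory symptoms are given date terms, leave baseline out: WURSS-21 is completed only between V1 and V2, so no V1 value exists.

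The cost is a line or two of analysis text and no new data. Baseline and sex use one degree of freedom each and the date terms two, so at most 4 of the 68 residual degrees of freedom (72 completers less 4 cells).
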